10.3. Appendix 3: Study Phases and Treatment Emergent Adverse Events

10.3.1. Study Phases for Concomitant Medication

The following rules will be used to classify a concomitant medication as being taken during one or more study treatment phases (pre-treatment, on-treatment and post-treatment):

Study Phase	Definition		
	Pre-Treatment	On-Treatment	Post-Treatment
Subject did not take study treatment (e.g, screen failures) and conmed stop date > date of Screening or variable that asks if conmed is on-going (refer hereafter as goingmed) is "yes"	Y		
(Conmed start date < treatment start date or variable that asks if medication taken prior to study is "yes" (refer hereafter as priormed)) and date of Screening < conmed stop date < treatment start date	Y		
(Conmed start date < treatment start date or priormed is yes) and treatment start date ≤ conmed stop date ≤ treatment stop date	Y	Y	
(Conmed start date < treatment start date or priormed is yes) and (conmed stop date > treatment stop date or goingmed is "yes")	Y	Y	Y
(Treatment start date ≤ conmed start date < treatment stop date and treatment start date ≤ conmed stop date ≤ treatment stop date) or (Treatment start date = conmed start date = conmed stop date = treatment stop date)		Y	
([Treatment start date ≤ conmed start date < treatment stop date] or [Treatment start date = conmed start date = treatment stop date]) and (conmed stop date > treatment stop date or goingmed is Yes)		Y	Y
Conmed start ≥ treatment stop date and treatment start date ≠ treatment stop date			Y

1. NOTES:

- The duration of a single concomitant medication can extend over multiple study phases
- Please refer to [Appendix 6: Reporting Standards for Missing Data](#) for handling of partial dates for concomitant medication.
- Note: If priormed or goingmed flags are missing or inconsistent, then medications will be assigned to all applicable phases.

10.3.2. Study Phases for Adverse Events and All Other Data Recorded in Logs (excluding Concomitant Medications)

Study Phase	Definition
Pre-Treatment	Date < Study Treatment Start Date
On-Treatment	Study Treatment Start Date ≤ Date ≤ Study Treatment Stop Date + 1
Post-Treatment	Date > Study Treatment Stop Date + 1

10.3.3. Treatment Emergent Flag for Adverse Events and Exacerbations

Flag	Definition
Treatment Emergent	
 If AE onset date is on or after treatment start date & on or before treatment stop date plus one day. Study Treatment Start Date ≤ AE Start Date ≤ Study Treatment Stop Date + 1.

NOTES:

- If the study treatment stop date is missing, then the AE will be considered to be On-Treatment.
- Time of study treatment dosing and start/stop time of AEs should be considered, if collected.

10.4. Appendix 4: Data Display Standards & Handling Conventions

10.4.1. Reporting Process

Software	

 The currently supported versions of SAS software will be used. 	
Reporting Area	
HARP Server	: uk1salx00175
HARP Compound	: gsk573719_gw642444/mid201749/final
Analysis Datasets	

 Analysis datasets will be created according to CDISC standards (SDTM IG Version 3.2 & ADaM IG Version 1.0 or higher]. For creation of ADaM datasets (ADCM/ADAE), the same version of dictionary datasets will be implemented for conversion from SI to SDTM. 	
Generation of RTF Files	

 RTF files will be generated for all tables in the final reporting effort for use in writing the CSR. 	

10.4.2. Reporting Standards

General

 The current GSK Integrated Data Standards Library (IDSL) will be applied for reporting, unless otherwise stated (IDSL Standards Location: https://spope.gsk.com/sites/IDSLLibrary/SitePages/Home.aspx): 
 4.03 to 4.23: General Principles 5.01 to 5.08: Principles Related to Data Listings 6.01 to 6.11: Principles Related to Summary Tables 7.01 to 7.13: Principles Related to Graphics
Formats

 All data will be reported according to the randomised treatment the subject received unless otherwise stated. GSK IDSL Statistical Principles (5.03 & 6.06.3) for decimal places (DP's) will be adopted for reporting of data based on the raw data collected, unless otherwise stated. Numeric data will be reported at the precision collected on the eCRF. The reported precision from non eCRF sources will follow the IDSL statistical principles but may be adjusted to a clinically interpretable number of DP's. 
 FEV₁, FVC and IC will have a min and max to 2dp and then follow IDSL standards to reporting other summary statistics SGRQ and TDI will have a min and max to 1dp and then follow IDSL standards to reporting other summary statistics CAT will have a min and max to 0dp and then follow IDSL standards to reporting other summary statistics Odds Ratios and Hazard Ratios will be reported to 2dp

Planned and Actual Time	

 • Reporting for tables, figures and formal statistical analyses: 
 • Planned time relative to dosing will be used in figures, summaries, statistical analyses and calculation of any derived parameters, unless otherwise stated. Actual time will be used for calculation of times to events and Kaplan-Meier plots. • The impact of any major deviation from the planned assessment times and/or scheduled visit days on the analyses and interpretation of the results will be assessed as appropriate. • Reporting for Data Listings: 
 • Planned and actual time relative to study drug dosing will be shown in listings (Refer to IDSL Statistical Principle 5.05.1). • Unscheduled or unplanned readings will be presented within the subject's listings. 	
Unscheduled Visits	

 • Unscheduled visits will only be included in summary tables as part of 'minimum/maximum post baseline' and 'minimum/maximum change from baseline' summary. • Unscheduled visits will not be included in figures. • All unscheduled visits will be included in listings. 	
Descriptive Summary Statistics	
Continuous Data	Refer to IDSL Statistical Principle 6.06.1
Categorical Data	N, n, frequency, %
Graphical Displays	

 • Refer to IDSL Statistical Principles 7.01 to 7.13. 	

10.5. Appendix 5: Derived and Transformed Data

10.5.1. General

Study Day

 Calculated as the number of days from randomisation date : 
 Ref Date = Missing → Study Day = Missing Ref Date < treatment start date → Study Day = Ref Date – treatment start date Ref Date ≥ treatment start date → Study Day = Ref Date – (treatment start date) + 1

Completer

 A study completer will be defined as a subject who completes the visit 5 trough FEV1 assessment.

10.5.2. Study Population

Demographics
Age

 Since the eCRF only collects the year of birth, GSK standard IDSL algorithms will be used for calculating age where date and month will be imputed as '30th June'. Birth date will be presented in listings as 'YYYY'. Age will be calculated based on the Pre-screening visit date.
Age Category

 Age categories are based on age at Pre-screening and are defined as: 
 ≤64 years 65-74 years 75-84 years ≥85 years
Body Mass Index (BMI)

 Calculated as Weight (kg) / Height (m)²

Smoking Status

 Smoking status at Screening is determined directly from the eCRF.

Maintenance Naive/Non Maintenance Naive

 Maintenance naive (MN) is defined as subjects with no COPD maintenance medication apart from short-acting bronchodilators recorded in the 30 days prior to screening (evaluation period 30 days prior to screening until 1st study treatment).

Reversibility and GOLD Classifications
Reversibility

 • A subject's responsiveness to salbutamol at Screening will be classified as 'Reversible' or 'Non-reversible' based on the difference between their pre-salbutamol assessment of FEV₁ and their post-salbutamol assessment of FEV₁ as follows: 
 • Reversible, if they had a difference in FEV₁ of $\geq 12\%$ and ≥ 200 mL, or • Non-reversible, if they had a difference in FEV₁ of < 200 mL or a ≥ 200 mL difference that was $< 12\%$ of the pre-salbutamol FEV₁.
GOLD Grade 1-4

Based on the Global Initiative for Chronic Obstructive Lung Disease (GOLD, 2018), Subjects will be classified into GOLD Grades 1-4 using the post-salbutamol percent predicted FEV₁ assessment at Screening (Visit 1):
 
 • GOLD Grade 1 (Mild): Percent Predicted FEV₁ $\geq 80\%$ • GOLD Grade 2 (Moderate): $50\% \leq$ Percent Predicted FEV₁ $< 80\%$ • GOLD Grade 3 (Severe): $30\% \leq$ Percent Predicted FEV₁ $< 50\%$ • GOLD Grade 4 (Very Severe): Percent Predicted FEV₁ $< 30\%$
GOLD Category A-D (Using CAT)

GOLD (CAT) Category A-D definitions as follows:
 
 A. Low risk, less symptoms: CAT < 10; ≤ 1 moderate exacerbation; and no hospitalizations for exacerbations, prior year. B. Low risk, more symptoms: CAT ≥ 10; ≤ 1 moderate exacerbation and no hospitalizations for exacerbations, prior year C. High risk, less symptoms: CAT < 10; ≥ 2 moderate exacerbations, prior year OR ≥ 1 leading to COPD hospitalization, prior year D. High risk, more symptoms: CAT ≥ 10; ≥ 2 moderate exacerbations, prior year OR ≥ 1 leading COPD hospitalization, prior year
Long-acting Bronchodilator Usage During the Run-in (Randomisation Stratum)

Randomization stratum, long-acting bronchodilator usage during the run-in, will be derived based on the RMC classification and will be grouped into the following 2 categories:
 
 • None • One long-acting bronchodilator per day 
Long-acting bronchodilator is defined as any COPD medication in Respiratory Medication Class (MRC) under 'Long-acting beta-2 agonist – Group 2' or 'Long-acting beta-2 agonist – Group 3' or 'Long-acting anticholinergic'.
 
Randomisation stratum is also collected at randomization in RAMOS NG and on eCRF. All randomisation stratum (RANDALL NG, eCRF and derived) will be listed.

Compliance
ELLIPTA DPI Compliance

The number of doses of study treatment taken by each subject from each inhaler will be calculated from the dose counter start and stop counts for each inhaler used. If a dose counter start count is missing then it will be assumed to be 30. If all dose counter stop counts are non-missing then the percentage compliance will be calculated as:
 
Compliance = $\frac{\text{sum of all (dose counter start – dose counter stop)} \times 100}{(\text{exposure stop date} – \text{exposure start date} + 1)}$
 
 • If any dose counter stop is missing then the treatment compliance will be set to missing for that subject. • If the dose counter start=dose counter stop then it will be assumed that no doses were taken from that container.
DISKUS Compliance

The number of doses of study treatment taken by each subject from each inhaler will be calculated from the dose counter start and stop counts for each inhaler used. If a dose counter start count is missing then it will be assumed to be 60. If all dose counter stop counts are non-missing then the percentage compliance will be calculated as:
 
Compliance = $\frac{\text{sum of all (capsules dispensed –capsules returned)} \times 100}{2 \times (\text{exposure stop date} – \text{exposure start date} + 1)}$
 
 • If any dose counter stop is missing then the treatment compliance will be set to missing for that subject.
Overall Compliance

 • The average of the compliance with the ELLIPTA DPI and compliance with the DISKUS. If the compliance with any of the two inhalers is missing then the overall compliance for that subject will be considered missing. • Overall compliance and compliance with each type of inhaler will be categorised as follows: 
 < 80 % ≥ 80 % to < 95 % ≥ 95 % to ≤105 % >105 % to ≤120 % >120 %. • If a subject received a treatment other than the randomized treatment during the study, the compliance will still be calculated using data from all containers received and overall exposure start and stop dates.

Cardiovascular Risk Factors

 • Subjects with at least one of the following current or past medical conditions at Screening will be classed as having a cardiovascular (CV) risk factor. The number of CV risk factors at Screening (0, 1, or >=2) will be derived.

Cardiovascular Risk Factors

 • Coronary artery disease • Myocardial infarction • Arrhythmia • Congestive heart failure • Hypertension • Cerebrovascular accident • Diabetes mellitus • Hypercholesterolemia
Concomitant Medications and COPD Exacerbation History
COPD Concomitant medications

COPD concomitant medications given for an exacerbation will be grouped into the following RMCs based on pre-defined code lists derived from ATC classifications:
 
 • Androgens and Estrogens • Anti-IgE, Anti-IL5 • Anticholinergic • Antiinfectives (antibiotics, antiseptics) • Antimycotics • Antivirals • Short-acting anticholinergic • Short-acting beta-2 agonist • Long-acting anticholinergic • Long-acting beta-2 agonist • Xanthine • PDE4 Inhibitors • Corticosteroid - inhaled • Corticosteroid - depot • Corticosteroid - systemic oral parenteral and intra-articular • Corticosteroid - other • Leukotriene receptor antagonist • Nedocromil or cromolyn sodium • Mucolytics • Oxygen • Other medication given for exacerbation • Other COPD medication
COPD Exacerbation History

 • Number of COPD exacerbations reported in the past year prior to Screening will be summarised (0, 1, =>2) according to the following categories: mild COPD exacerbation, moderate COPD exacerbation, severe COPD exacerbation, mild/moderate/severe COPD exacerbation, moderate/severe COPD exacerbation and severe COPD exacerbation. • Moderate COPD exacerbations are defined as exacerbation that required treatment with oral/systemic corticosteroids and/or antibiotics (not involving hospitalisation). • Severe COPD exacerbations are defined as exacerbations that required in-patient hospitalisation.

Concomitant Medications and COPD Exacerbation History

 Total number of mild/moderate/severe COPD exacerbations are defined as total numbers of mild, moderate and severe COPD exacerbation for each subject. Total number of moderate/severe COPD exacerbations are defined as total numbers of moderate and severe COPD exacerbation for each subject.

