2. SUMMARY OF KEY PROTOCOL INFORMATION

2.1. Changes to the Protocol Defined Statistical Analysis Plan

Changes from the originally planned statistical analysis specified in the protocol are outlined in [Table 1](#).

Table 1 Changes to Protocol Defined Analysis Plan

Protocol	Reporting & Analysis Plan	
Statistical Analysis Plan	Statistical Analysis Plan	Rationale for Changes
	
 An additional population has been defined, the Activity Monitoring (AM) Population, which will comprise all subjects in the ITT population who provide data from at least one activity monitoring session. 	
 Population needed for subset of subjects participating in Activity Monitoring.
	
 All other Endpoints promoted to secondary endpoints 	
 Study aims have developed since protocol and thus previous endpoints classed as 'other' have further importance
	
 An analysis by Maintenance Naive (MN) and Non-Maintenance Naive subgroups have been included. 	
 To investigate prospectively the 1st line use of LAMA/LABA in all symptomatic subjects (no existing data the literature to our knowledge)
	
 An analysis of ratio of trough FEV1 to baseline trough FEV1 	
 To investigate trough FEV1 ratio change from baseline

 Intent-to-treat ICS free (ITT ICS free) 	
 Population excluded. 	
 G-BA analysis to be conducted on the ITT population due to a change in G-BA guidance.

 To compare albuterol/salbutamol use captured in the eDiary with the electronic metered dose inhaler (eMDI) Device as data allow 	
 Not included in this RAP. 	
 Will be included in a supplementary RAP if deemed necessary.

Protocol	Reporting & Analysis Plan	
Statistical Analysis Plan	Statistical Analysis Plan	Rationale for Changes

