2.3. Study Design

Overview of Key Study Design Features	
Design Features:	
 • Multi-centre, randomized, double blind, double dummy, 3-arm parallel group study to compare Umeclidinium/Vilanterol, Umeclidinium, and Salmeterol in subjects with chronic obstructive pulmonary disease (COPD). • Approximately 3232 subjects will be screened, such that 2424 subjects will be randomized and approximately 2181 evaluable subjects complete the study. • Eligible subjects will be stratified by country, long-acting bronchodilator usage during the run-in (none or one long-acting bronchodilator per day) and activity subset (activity subset or no activity subset), and randomized in a ratio of 1:1:1 to UMEC/VI inhalation powder (62.5/25 mcg once daily) administered via the ELLIPTA inhaler, or UMEC (62.5 mcg once daily) administered via the ELLIPTA or salmeterol (50 mcg BID) administered via the DISKUS. Note the activity subset was only included as a randomisation stratification group for logistical purposes. • A subset of subjects up to 150 per treatment arm will undergo assessment of their physical activity measured through a physical activity monitor (Actigraph GT9X) worn for 7 days from Screening (Visit 1), for 7 days from Randomisation (Visit 2), 7 days from Visit 3, and for 7 days prior to last clinic Visit (Visit 5). • The total duration of subject participation in the study will be approximately 29 to 35 weeks consisting of 6 weeks pre-screening if necessary, 4 weeks run-in, 24 week treatment and one week Follow-Up.
Dosing :	
 • The following study medications will be used in this study: 
 - UMEC/VI 62.5/ 25mcg administered via ELLIPTA - UMEC 62.5 mcg administered via ELLIPTA - Salmeterol 50 mcg administered via DISKUS - Placebo via ELLIPTA - Placebo via DISKUS 
Subjects will be instructed to take one dose of medication each morning from the ELLIPTA (one inhalation equals one dose), and one dose in the morning and one in the evening from the DISKUS.
 
The ELLIPTA will provide a total of 30 doses and the DISKUS will provide a total of 60 doses.

Overview of Key Study Design Features	

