6.1.3. Concomitant Medications

Medications that have been stopped prior to Screening will be listed and not be included in any summary tables.

Medications not taken for an exacerbation will be summarised by Anatomical-Therapeutic-Chemical (ATC) level 1 and ingredient. COPD medications given for an exacerbation will be summarised by Respiratory Medication Class (RMC).

Medications taken for an exacerbation and those not taken for an exacerbation will be listed separately. Both listings will indicate in which study phases each medication was taken (pre-treatment and/or on- treatment and/or post-treatment)

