7.4. Subgroup Analyses

Subgroup Analysis
Endpoints

Repeat specified analyses/displays for:
 
 • Study Population • Efficacy • Safety 
Output for subgroup analysis indicated in Section 10.8.8

Model Specification

 • Analysis will be performed 'by' each subgroup separately. Please refer to main endpoint model for model specification.
Model Checking & Diagnostics

 • As per main endpoint
Model Results Presentation

 • As per main endpoint

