Day	-70 to -28	-28	1	28	84	168		7 days after V5 or EW Visit
Window	-7/+2 days	-7/+2 days	-7/+2 days	-7/+2 days	-7/+2 days	-7/+2 days		±3 days
Collect eDiary						X	X	
Dispense study treatment ¹¹			X	X	X			
Collect study treatment				X	X	X	X	
Assess study treatment compliance during treatment ¹⁰				X	X	X	X	
Study sub-set								
Physical activity monitor ¹²		X	X	X		X		
Collect Physical activity monitor						X	X	

1. Pre-screen Visit 0 must be completed prior to Screening Visit1. It can be completed 6 weeks prior or on the same day of V1, if no wash out of exclusionary medications is required.
2. Early Withdrawal Visit: Subjects that withdraw should return to the clinic as soon as possible to complete the Early Withdrawal Visit procedures.
3. Spirometry at screening should be performed as described in (Section 7.2.2.1 in the protocol).
4. SAC BDI, SAC TDI, SGRQ-C, CAT questionnaires will be completed at clinic visits and in the eDiary
5. EXACT/ER-S: COPD is completed daily in the eDiary approximately 2 hours before bed-time, starting on Day 1 of the run-in period.
6. For the start date of collecting AEs and SAEs see (Appendix 4)
7. Pregnancy test: for females for child bearing potential only.
8. Pharmacogenetic sample may be drawn at visit 2 or any visit after.
9. Rescue medication use to be recorded in the eDiary daily **and** in some sites in the eDiary and the eMDI
10. Sites are requested to call subjects every 2 weeks to remind them to take study treatment regularly and to record the time of the morning and evening dose in the eDiary.
11. In order to ensure subjects have sufficient doses of study treatment, they must return to clinic within 30 days from V2 and within 60 days from V3 respectively.
12. The Actigraph GT9X should be worn for 7 days from Visit 1, for 7 days from Visit 2, for 7 days from Visit 3 and for 7 days prior to Visit 5.

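### The maintenance-naive look-back (30 days before Screening) is shorter than the longest pre-screen washout interval the SAP allows (42 days), so recently treated subjects can be classed as naive

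*SAP*

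**What the plan says.** **Definition.** SAP 10.5.2 reads: "Maintenance naive (MN) is defined as subjects with no COPD maintenance medication apart from short-acting bronchodilators recorded in the 30 days prior to screening". The bracket that follows sets the end of the evaluation period at first study treatment. The window therefore runs from 30 days before Screening to first dose.

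**Pre-screen interval.** Section 2.3 gives the length of participation as "approximately 29 to 35 weeks consisting of 6 weeks pre-screening if necessary, 4 weeks run-in, 24 week treatment and one week Follow-Up". The schedule in 10.1.1 places Visit 0 at Day -70 to -28 and Visit 1 at Day -28. Its first footnote explains the timing of Visit 0: "It can be completed 6 weeks prior or on the same day of V1, if no wash out of exclusionary medications is required".

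**Purpose and analysis.** Table 1 in section 2.1 gives the reason for adding the subgroup: "To investigate prospectively the 1st line use of LAMA/LABA in all symptomatic subjects". Section 7.4 adds: "Analysis will be performed 'by' each subgroup separately".

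**Earlier medication.** Section 6.1.3 says: "Medications that have been stopped prior to Screening will be listed and not be included in any summary tables".

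**The concern.** The time between Visit 0 and Visit 1 exists so that a subject can come off exclusionary medication. If one of those medications is COPD maintenance therapy and the washout lasts more than 30 days, the last dose falls before the MN window opens. The subject then counts as never having been on maintenance treatment, although it was stopped in order to enter the trial.

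Such a subject is not a first-line patient, and baseline lung function and symptoms were measured after treatment had been withdrawn. Each subgroup is analysed separately, so these subjects would enter the MN estimates directly. The displays that use MN status are those in 10.8.10: study population tables 1.33 to 1.44, efficacy tables 2.78 to 2.133, efficacy figures 2.48 to 2.70 and safety tables 3.34 to 3.42.

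**Working it through.** **Inputs**
- MN look-back: 30 days before Screening, continuing to first dose (10.5.2).
- Visit 0 at Day -70 to -28; Visit 1 at Day -28; window of -7/+2 days on each (10.1.1).
- Participation of 29 to 35 weeks (2.3).

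**1. Reproduce the stated duration.** Without pre-screening: 4 + 24 + 1 = 29 weeks. With it: 6 + 4 + 24 + 1 = 35 weeks. Both match, so six weeks is the longest nominal pre-screen interval, not a fixed one.

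**2. Longest interval in days.** -28 − (-70) = 42 days.

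**3. Part not covered.** The MN window opens at Day -28 − 30 = Day -58. The uncovered part is 42 − 30 = 12 days, that is, 42 to 31 days before Visit 1 (Days -70 to -59).

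**4. Effect of visit windows.** Assume that the two windows act independently and that Visit 0 is planned the full six weeks ahead.
- Shortest interval: (-28 − 7) − (-70 + 2) = 33 days, a gap of 3 days.
- Longest interval: (-28 + 2) − (-70 − 7) = 51 days, a gap of 21 days.

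**5. Who is missed.** This applies to subjects with no other maintenance drug up to first dose.

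| Last dose before Visit 1 | Class under 10.5.2 |
|---|---|
| 14, 21, 28 or 30 days | non-MN |
| 35 or 42 days | MN |

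**6. Could screening mean Visit 0?** No. Section 10.5.2 itself separates the two: age is taken at the pre-screening visit, and GOLD grade at Screening, identified there as Visit 1.

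**7. Does anything else in the SAP correct it?**
- The bracket extends the window forward only; its start stays 30 days before Screening.
- The run-in stratum puts such a subject under none, together with the truly naive, so adjusting for stratum does not separate them.
- Drugs stopped before Screening stay out of the summary tables (6.1.3), and for treated subjects the pre-treatment phase in 10.3.1 requires a stop date after Screening. They do appear in listings.
- No section says that a drug stopped for study washout makes a subject non-naive.

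**8. Size of any bias.** Let m be the fraction of the MN group that was washed out, and let θ_N and θ_W be the treatment effects in truly naive and washed-out subjects. The MN estimate targets (1 − m)θ_N + mθ_W, a shift of m(θ_W − θ_N). The SAP gives none of these quantities. If m were 10% to 30% (purely an assumption), the shift would be 10% to 30% of the difference in effects. It is zero if m is zero or if the two effects are equal.

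**The case against.** The strongest reply is that the group at risk is narrow and may be empty. A subject whose last dose was 30 days or less before Visit 1 is already non-MN, and so is anyone who takes a maintenance drug at any time up to first dose. Run-in allows one long-acting bronchodilator, so a subject who drops one drug but continues another is classed correctly. The SAP does not say which medications are exclusionary, whether any is COPD maintenance therapy, or whether any needs more than 30 days. All of this stands, and it limits the point to a possible contamination of unknown size.

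A second reply is that any finite look-back admits some past users, so its length is a design choice. That is partly right. The objection here is narrower: the look-back is shorter than the interval this trial sets aside for stopping treatment.

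A reader might go further and infer that patients taken off maintenance therapy for the trial are in general counted as naive, or that the first-line question is answered in the wrong patients. The SAP does not support either reading, because six weeks is a ceiling used if necessary and shorter washouts are caught. A reader might also infer a known dilution of the MN versus non-MN contrast by a factor of 1 − m. That contrast is not a planned analysis: the subgroups are analysed separately, the MN displays list no interaction test, and m is not given. Nor would the cases be hidden, because medications stopped before Screening are listed.

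**Conclusion.** The definition has a gap on the SAP's own figures: 12 nominal days, or 3 to 21 days under the visit-window assumption above when Visit 0 is planned six weeks ahead. Subjects whose sole maintenance drug was last taken in that gap are labelled naive, which conflicts with the first-line purpose of the subgroup.

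How many such subjects exist cannot be derived from the SAP and may be none. Bias in the treatment comparison within MN also requires that washed-out subjects respond differently from naive ones, which is plausible but not shown. The primary analysis and all whole-ITT analyses do not use MN status and are unaffected. The point is worth correcting because the subgroup is meant to answer a specific question and the correction is small.

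**What to change.** In 10.5.2, start the MN evaluation period at the earlier of Visit 0 and 30 days before Visit 1, and end it at first study treatment as now. Any COPD maintenance medication other than a short-acting bronchodilator recorded as taken on or after Visit 0 then makes the subject non-MN. Report with Table 1.35 how many subjects change class compared with the present definition. If none do, that shows that this gap did not affect the subgroup.

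This is preferable to a fixed 42 days, because visit windows could stretch the interval to 51 days. It is also preferable to a look-back of 30 days before Visit 0: that would vary from 30 to 42 + 30 = 72 days before Visit 1 according to scheduling, and could reach further back than medication was collected.

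The cost is one sentence, one derivation and one added count. Concomitant medication is already assessed at Visit 0, so no new collection is needed. The MN subgroup may become slightly smaller, with slightly wider intervals. The window still varies with the date of Visit 0, but only so as to capture treatment stopped after the subject entered pre-screening.
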